7.1.1.9 Death

All AEs resulting in death either during the study period or within 6 months after dosing must be reported as a SAE.

The convention for recording death is as follows:

- AE term: lead cause of death (e.g. multiple organ failure, pneumonia, myocardial infarction),
- Outcome: fatal.

The only exception is if the cause of death is unknown (i.e. sudden or unexplained death), in which case the AE term may be "death" or "sudden death".

7.1.1.10 Reporting to Competent Authorities, IECs/IRBs and other Investigators

The Sponsor will ensure that processes are in place for submission of reports of SUSARs occurring during the study to the CAs, Independent Ethics Committees (IECs)/Institutional Review Boards (IRBs) and other Investigators concerned by the IMP.

Reporting will be done in accordance with the applicable regulatory requirements. The Sponsor must report all SUSARs to EMA's EudraVigilance database within 15 days.

Fatal and life-threatening SUSARs should be reported within 7 calendar days, with another 8 days for completion of the report.

The Sponsor can prepare additional reports for other authorities (e.g. FDA).

7.1.2 Physical Examination

Physical examinations (including body weight (in light clothes and without shoes) and height measurements will be evaluated at screening and end-of-study visit (see Study Schedule of Events, Section 15.1).

Clinically significant changes, in the judgement of the Investigator, in physical examination findings will be recorded as AEs. Any physical examination findings (abnormalities) persisting at the end of the study will be followed by the Investigator until resolution or until reaching a clinically stable endpoint.

7.1.3 Vital Signs Assessments

After 5 min of rest, supine systolic and diastolic blood pressure (SBP & DBP), heart rate (HR) and body temperature (aural) will be assessed at screening and end-of-study visit (see Study Schedule of Events, Attachment #1_Section 15.1). In case of adverse events, additional vital signs assessments may be performed at the discretion of the Investigator.

7.1.4 Electrocardiograms Assessments

Twelve-lead computerised standard ECGs, with paper printout, will be obtained while subject is in resting supine position for at least 5 minutes and until four regular consecutive complexes are available, at screening and end-of-study (see Study Schedule of Events, Attachment #1_Section 15.1). In case of adverse events, additional ECG assessments may be performed at the discretion of the Investigator.

For each timepoint, computerised standard ECGs will be recorded so that the following parameter can be automatically calculated and reported on the ECG paper printout:

- Sinus rhythm,
- RR interval duration or heart rate (HR),
- PR interval duration,
- QRS interval duration,
- QT interval duration,
- QT interval corrected by the appropriate correction method (e.g.: Bazett).

Automated ECG interval data will be interpreted by a qualified Physician at the site as soon after the time of ECG collection as possible, and ideally while the subject is still present. The qualified Physician will document his/her review and interpretation (including evaluation of clinical significance in case of abnormality) on every ECG printout.

The paper printouts will be kept in the source documents at site. Only the interpretation and abnormalities will be reported in the eCRFs for integration with other clinical study data. These paper ECGs may be subject to further review, if appropriate.

Any clinically significant abnormalities will be recorded as AEs.

7.1.5 Clinical Safety Laboratory Tests

Blood and urine samples will be collected for standard clinical laboratory tests, including biochemistry, haematology, and urinalysis panels, as well as specific tests such as urine drug screening and alcohol tests (and urine/serum pregnancy tests for women of childbearing potential) at timepoints indicated in the Study Schedule of Events (see Attachment #1_Section 15.1).

The exact lists of parameters to be assessed are given in the Attachment #2_Section 15.2.

The results of laboratory tests performed during the screening phase must be obtained before dosing on Day 1.

7.1.5.1 Urinalysis

Freshly voided urine samples (at least 10 ml) will be collected to perform a dipstick assessment of the parameters described in Attachment #2 Section 15.2.

Microscopy will be performed, if indicated, but results will not be collected in the eCRF. If in the opinion of the Investigator there are any clinically significant abnormalities in microscopy, they will be recorded as an AE in the eCRF.

7.1.5.2 Pregnancy Test

A Beta-human chorionic gonadotrophin (ßHCG) serum test will be performed for all female subjects of childbearing potential at Screening (visit 1) and if clinically indicated thereafter. Human chorionic gonadotrophin (HCG) urine test will also be performed on Day-1 (baseline) and at the end-of-study visit. It may be repeated at any time during the study according to Investigator's judgement.

Any subject becoming pregnant during the study will be withdrawn. All pregnancies that occur during the study are to be reported as described in Section 7.1.1.8.

7.1.5.3 Investigator's Review

Investigators must document their review of each laboratory report by signing or initialling and dating each report. Laboratory values that fall outside a clinically accepted reference range or values that differ significantly from previous values will be evaluated.

When multiple laboratory values are out of range but not clinically significant, "all labs NCS" or a general comment may be written on the laboratory page. However, all clinically significant laboratory values must be individually marked with CS.

The Investigator will review the safety laboratory test results, document the review, and record any clinically relevant changes occurring or observed during the study in the AE section of the eCRF (see Section 7.1.1 for abnormal laboratory tests that should be recorded as AEs).

All clinically relevant abnormal laboratory tests occurring during the study will be repeated at appropriate intervals until they return to Baseline or to a level deemed acceptable by the Investigator and the Sponsor's clinical monitor (or his/her designated representative) or until the abnormality is explained by an appropriate diagnosis.

7.1.5.4 Sample Handling, Storage and Destruction

Full details related to the samples processing, labelling, storage, shipment and destruction procedures will be provided to the Investigator via separate instructions and archived in the Trial Master File (TMF).

Samples collected for specified laboratory tests will be destroyed within 60 days of receipt of confirmed test results. Tests are run and confirmed promptly whenever scientifically appropriate. When scientific circumstances warrant, however, it is acceptable to retain samples to batch the tests run, or to retain the samples until the end of the study to confirm that the results are valid. Certain samples may be retained for a longer period, if necessary, to comply with applicable laws, regulations, or laboratory certification standards.

7.1.6 Additional Definitions or Special Procedures

Not applicable.

7.2 Efficacy Assessment(s)

Not applicable.

7.3 Assessments of lead levels and other elemental impurities

The assessment of elemental impurities in blood and urine include lead and 8 other elemental impurities: i.e. arsenic, cadmium, mercury, cobalt, vanadium, nickel, barium and aluminium. Other impurities may be assessed via Biobanking samples (See Attachment #5 Section 15.5).

7.3.1 Sampling Schedule

Urine collections (as 24-hour collection) and Blood samples for the measurement of elemental impurities will be collected as described in the Schedule of events (see Attachment #1_Section 15.1).

During the outpatient visits, blood samples will be collected pre-dose of any of the 3 dosing occasions of that day.

Taken into account the time window flexibility during the Day 35, the 24-hour urine collection should be done whilst subject is still under study treatment (e.g.: if subject performs the Day 35 at Day 36, Smecta® will be given until the evening of Day 36, or alternatively if subject comes at Day 34, the last Smecta® intake will be done at Day 34 evening).

7.3.2 Sampling Method for Pharmacokinetic Measurements

Blood samples (8 ml at each time point) will be collected as described in the Schedule of event (see Attachment #1 Section 15.1):

- For determination of lead in blood and 8 other elemental impurities in blood (arsenic, cadmium, mercury, cobalt, vanadium, nickel, barium and aluminium)
- Biobanking samples (blood): for potential assessment of other elemental impurities levels in blood
- Biobanking samples (serum): for potential assessment of lithium levels in serum

- Biobanking samples (plasma): for potential determination of lead in the plasma.

. During the study, the nominal sample collection times may be adjusted, but the total number of samples will not increase. The exact dates and times of blood sample collection, and Smecta® administration must be recorded in the eCRF.

Specific blood collection, preparation and storage conditions are described in a separate Study Laboratory Manual.

All urine samples collected over the specific 24-hour interval will be pooled and the total urine volume measured and recorded in the eCRF. From this pooled volume, 2 aliquots of 1.5 ml (primary, back-up) each will be obtained for the measurement of elemental impurities. Two additional urine aliquots of 1.5 ml (1 primary, 1 back-up) will be collected for the biobanking purpose.

Each tube should be labelled in accordance with the Sponsor's requirements. Aliquots will be shipped on dry ice.

Unless specified below, specific details of labelling, sampling, storing and shipping procedures will be described in separate documentation, and provided by the Sponsor.

7.3.3 Bio-analytical Method

Blood and urine samples will be analysed to determine concentrations of elemental impurities using a validated, specific and sensitive ICP-MS method by Quality Assistance (Donstiennes, Belgium). Assessment of lead and each elementary impurity in blood and urine will be performed under the supervision of Ipsen Pharmacokinetics and Drug Metabolism (PDM) Department.

7.3.4 Parameter Estimation

Individual blood concentrations for each elementary impurities will be listed and summarised by timepoint using descriptive statistics for continuous variables (number of available observations, mean, median, standard deviation (SD), minimum, maximum, geometric mean, and geometric coefficient of variation assuming log-normally distributed data).

PK parameters of lead may be calculated if feasible.

Change from baseline by timepoint will be assessed and summarised using descriptive statistics.

Individual urine concentrations for each elementary impurities will be listed and summarised by timepoint using descriptive statistics. Change from baseline by timepoint will be assessed and summarised using descriptive statistics

Descriptive summary statistics (the number of observations (n), mean, median, SD and range for continuous variables, and n and percentage (%) for categorical/nominal variables) will be presented.

7.4 Pharmacodynamic Assessment(s)

No pharmacodynamic assessment will be performed during this study.

7.5 Exploratory Assessment(s)

Single faces samples will be collected at timepoint defined in the schedule of events (see Attachment #1_Section 15.1) and processed according to standardised techniques developed by an international consortium (International Human Microbiome Standards, IHMS, http://www.microbiome-standards.org/#). Detailed procedures for the collection, handling, storage, shipment and analyses of the samples will be described in the specific study manual. The stools samples taken after the end of the treatment period (e.g. from Day 65 to Day 125 visits) will be analysed only in case of a significant change of microbiota is observed during

the study treatment in order to assess the resilience (return to the baseline profile) of microbiota during the post study treatment period.

Consistency of stools (recorded and rated according to Bristol scale) (See attachment # 7_ Section15.7) and frequency will be assessed over 24h by the subject the day before Screening, Day-14, baseline (D-1), Day 8, Day 35, Day 65, Day 95 and Day 125 visits, collected in a diary and reported by the site in the eCRF.

7.6 Compliance to Study Procedures

7.6.1 Compliance to Protocol

Every attempt will be made to select subjects who have the ability to understand and comply with instructions. Noncompliant subjects may be discontinued from the study. The time and day of drug administration will be recorded by the study site when present at the clinical unit and by the subject when self-administered (using Subject Diary). These will be recorded in the eCRF by the site. Drug accountability records will be maintained by the study site.

7.6.2 Compliance to Timing of Procedures

The specifications in this protocol for the timings and dates of primary tests are given as targets, to be achieved within reasonable limits. The scheduled time points may be subject to minor deviations within the allowed time windows specified in the Study Schedule of Events (see Section 15.1); however, the actual time must always be correctly recorded in the eCRF and other relevant source documents. Any excursion outside of these allowed time windows might be regarded as protocol violation.

Any major modification that might affect the conduct of the study, subject safety, and/or data integrity will be detailed in a protocol amendment.

8 STATISTICAL ANALYSES

8.1 Data Analysis Plan

8.1.1 General Considerations

Statistical analysis will be performed by a Sponsor selected CRO and according to ICH E9 guidelines and using SAS version 9.3 or higher (See references in Section 14).

8.1.2 Determination of Sample Size

The critical limit of $50\mu g/l$ of lead is chosen as being the most conservative value taken among various guidelines (risk of saturnism, observations under high lead exposure at work). The baseline blood lead concentration of $31,4\mu g/l$ is considered as being a mean blood lead concentration in a survey of 1949 adults (18-74 years old) living in France in 2006-2007 (Falq et al. 2011). This population is representative of the French population including different socio-demographic characteristics and environment risk factors such as: sex, age, smoking status, type of drinking water, leisure activities, age of housing, shellfish/crustacean consumption. Considering the inclusion and exclusion criteria defined for the study, the enrolled subjects should have BLL levels in the same range as reported in the survey.

With a standard error to the mean of [0,56], the mean blood lead concentration of 31.4 μ g/l is at confidence 95% to be found within [29.82; 32.98] under similar conditions. The non-superiority Δ margin is a clinical choice calculated as the difference of: $50 - 31.4 = 18.6 \mu$ g/l. A precision of 15% (CV) of the bioanalytical assay has been considered in the determination of sample size.

Based on the above considerations, a sample size of 29 subjects with baseline mean blood lead concentration no greater than 36 μ g/l (<36 μ g/l), is required to provide 81% power to reject the null hypothesis of a difference of means no greater than 18,6 μ g/l (\leq 18,6 μ g/l considered as no difference of means).

Considering potential drop-out, it is planned to enrol a total of 35 subjects to ensure that at least 29 subjects completed the study.

Subjects who prematurely discontinue after IMP administration will not be replaced.

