3.5 Rationale for the Study Design

Discussion of Design

The primary objective of the study is to investigate the Blood Lead Levels after the chronic oral administration of Smecta® in subjects suffering from chronic functional diarrhoea. In each subject, lead concentrations obtained at several occasions during and after dosing with Smecta® will be compared to each individual baseline data. Other elemental impurities levels will be assessed in blood comparatively to baseline. Moreover, 24h urine level of all these impurities will be collected and assessed by mean of validated analytical methods. Samples of biobanking will be collected for potential other elemental impurities assessments as well as the potential measurement of lead in plasma. Stools samples and the assessment of stool consistency and stool frequency will be also collected for microbiote assessment as ancillary study.

Considering the extensive distribution of lead in the body as well as its long term residence time, a post-treatment follow-up period of 3-months has been considered appropriate to detect any change in the elemental impurities within the frame of a chronic administration of Smecta®.

Dose Selection and Dosing Regimen

The dose of Diosmectite (i.e. 1 sachet (3g) TID) is the recommended dose for Smecta® in the indication of chronic diarrhoea in an adult population.

For the purpose of this study, and in order to potentially limit variability and increase the bioavailability of lead (higher at low pH) dosing of Smecta® will occur in condition of fast 30 minutes before breakfast, 1 hour before noon lunch and 1 hour before evening dinner.

Five (5) weeks can be considered as a repeated chronic administration as chronic diarrhoea is defined as usually lasting more than 4 weeks.

Population Selection and Sample Size

The targeted subject population to assess the primary endpoint are subjects with chronic functional diarrhoea, one of the indication of Smecta® with subjects treated daily for several weeks.

Indeed, lead absorption could be different in subjects with normal gastro-intestinal transit time from patients with various gastrointestinal disorders of organic origin. Moreover patient with acute diarrhoea require a treatment lasting usually for 3 to 7 days that is far from chronic condition

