1.3.4 Planned sample size

The critical limit of 50µg/l of lead is chosen as being the most conservative value taken among various guidelines (risk of saturnism, observations under high lead exposure at work). The baseline blood lead concentration of 31,4µg/l is considered as being a mean blood lead concentration in a survey of 1949 adults (18-74 years old) living in France in 2006-2007 (Falq et al. 2011). This population is representative of the French population including different socio-demographic characteristics and environment risk factors such as: sex, age, smoking status, type of drinking water, leisure activities, age of housing, shellfish/crustacean consumption. Considering the inclusion and exclusion criteria defined for the study, the enrolled subjects should have BLL levels in the same range as reported in the survey. With a standard error to the mean of [0,56], the mean blood lead concentration of 31.4µg/l is at confidence 95% to be found within [29.82; 32.98] under similar conditions. The non-superiority Δ margin is a clinical choice calculated as the difference of: 50 – 31.4 = 18.6µg/l. A precision of 15% (coefficient of variation) (CV) of the bioanalytical assay has been considered in the determination of sample size. Based on the above considerations, a sample size of 29 subjects with baseline mean blood lead concentration no greater than 36 µg/l (<36 µg/l), is required to provide 81% power to reject the null hypothesis of a difference of means no greater than 18,6 µg/l ($\leq 18,6 \mu\text{g/l}$ considered as no difference of means). Considering potential drop-out, it is planned to enroll a total of 35 subjects to ensure that at least 29 subjects completed the study.

Subjects who prematurely discontinue after investigational medicinal product (IMP) administration will not be replaced.

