3.1.1 Primary endpoint

The primary endpoint is to assess the absolute change in blood lead level (BLL) from baseline during treatment and post-treatment follow-up period.

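### The stated 81% power with 29 subjects rests on between-person spread in blood lead, while the endpoint is each subject's change from their own baseline, so it is not the power of this design

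*Protocol*

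**What the plan says.** Protocol 8.1.2 (Determination of Sample Size) takes its reference level from blood lead measured "in a survey of 1949 adults (18-74 years old) living in France in 2006-2007". It reports the survey's precision as "With a standard error to the mean of [0,56], the mean blood lead concentration of 31.4" µg/l, with a printed 95% interval of 29.82 to 32.98. The 18.6 µg/l "margin is a clinical choice calculated as the difference of" 50 and 31.4. A 15% assay CV is said to have been considered, without saying how. The conclusion is that "a sample size of 29 subjects with baseline mean blood lead concentration no greater than 36" µg/l "is required to provide 81% power to reject the null hypothesis". SAP 1.3.4 repeats the paragraph, saying that the sample "is required to provide 81% power to reject the null hypothesis of a difference of means". Neither document gives an SD, a test, an alpha level, sidedness or a within-subject correlation for this calculation.

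The endpoint is of a different kind. Protocol 3.5 says that in each subject "lead concentrations obtained at several occasions during and after dosing with Smecta® will be compared to each individual baseline data". SAP 3.1.1 defines the primary endpoint as the "absolute change in blood lead level (BLL) from baseline during treatment and post-treatment follow-up period". SAP Appendix 1 (5) sets the blood lead baseline as the average of the available screening and Day -1 values. There is one treatment group. SAP 3.1.6 plans no significance testing, and SAP 3.2.2.1 reports means with 95% confidence intervals.

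**The concern.** A survey standard error measures how much people differ from one another. Much of that difference cancels when each subject is compared with their own pre-dose values. What governs the precision of a mean change is the SD of the change, and the sample size paragraph has no term for it apart from assay error. If the 81% comes from between-person spread, it describes something other than the analysis planned.

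Two things are at stake. First, the trial exists to support a lead risk assessment (Protocol 1.7), and the reader is not told how small a rise in mean blood lead 29 subjects can exclude, or how wide the reported interval will be. Second, Protocol 8.2 and SAP 3.2.18 allow the sample size to be re-evaluated if pre-dose lead falls outside the survey interval. Repeating the same calculation would resize the trial on the wrong variance.

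**Working it through.** **Inputs from Protocol 8.1.2:** SE 0.56; survey n = 1949; mean 31.4; limit 50; margin 18.6; baseline mean condition 36; assay CV 15%; n = 29. **Assumed because not stated:** two-sided 5% (one-sided 2.5%).

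**Step 1: the implied SD.** 0.56 × √1949 = 24.72 µg/l, treating the survey as a simple sample. The printed interval does not agree with this: 31.4 ± 1.96 × 0.56 is 30.30 to 32.50. The printed half-width of 1.58 implies SE = 1.58/1.96 = 0.81 and SD = 0.806 × √1949 = 35.6. Both are between-person figures.

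**Step 2: reproducing 81%.**

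| Calculation at n = 29 | Power |
|---|---|
| Two independent groups of 29, difference 18.6, SD 24.72: 18.6/(24.72 × √(2/29)) − 1.96 = 0.905 | 81.7% (z), 80.4% (t) |
| Same, assay variance added: SD = √(24.72² + 4.71²) = 25.17 | 80.4% (z), 79.0% (t) |
| One sample, difference 50 − 36 = 14, assay variance at 50 µg/l added: SD = √(24.72² + 7.5²) = 25.84 | 83.1% (z), 80.4% (t) |
| One sample, difference 18.6, SD 35.6 | 80.4% (z), 77.5% (t) |
| One sample, difference 18.6, SD 24.72 | 98.2% (z), 97.4% (t) |

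The first row is the closest match: the z formula for 81% power returns 29 per group, and by t, 29 is the smallest group size reaching 80% (28 gives 78.9%). The next three rows also come near. All four use the spread between people.

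**Step 3: the paired design.** With equal correlation r between any two of a subject's values and a baseline that is the mean of two, SD of change = 24.72 × √(1.5 × (1 − r)). Half-width = 2.048 × SD/√29. Neither document gives r, so a range is shown.

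| Assumed r | SD of change (µg/l) | Power against 18.6 (t) | 95% CI half-width (µg/l) | Rise for 81% power (µg/l) |
|---|---|---|---|---|
| 0.5 | 21.4 | 99.5% | ±8.1 | 11.7 |
| 0.8 | 13.5 | >99.9% | ±5.2 | 7.4 |
| 0.9 | 9.6 | >99.9% | ±3.6 | 5.2 |
| 0.95 | 6.8 | >99.9% | ±2.6 | 3.7 |

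With a single baseline value, √(2 × (1 − r)) replaces √(1.5 × (1 − r)), and r = 0.5 gives SD 24.7 and power 97.4%.

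**Step 4: a floor from assay error alone.** At the mean level, SD of change = 0.15 × 31.4 × √1.5 = 5.8, half-width ±2.2. Allowing for the spread of levels, the root-mean-square level is √(31.4² + 24.72²) = 40.0, so SD = 0.15 × 40.0 × √1.5 = 7.3 and half-width ±2.8.

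**Step 5: what 81% would require.** In a paired t calculation with n = 29 and a difference of 18.6, 81% power corresponds to an SD of change of about 34.1 µg/l, which is larger than the assumed baseline mean of 31.4. On SD 24.72 with a single baseline and r = 0, the SD of change is 35.0 and power is 79.0%. So 81% is close to assuming that a subject's earlier lead level says nothing about the later one.

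**The case against.** The sponsor's method is not printed. A reader might infer from the close match that a two-group t-test was used for a one-group trial. The documents do not support that as fact: the one-sample route with a difference of 14 uses the 36 µg/l condition and the assay CV, both of which are printed, and gives 80.4% by t. The sponsor may simply have put a conservative SD into a single-group formula. This stands, and it makes the issue an undocumented and unsuitable variance rather than a proven slip of arithmetic.

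The paired figures rest on correlations found in neither document. If the SD is 35.6, r = 0.5 with the two-value baseline gives 88.0% power rather than 99.5%, and r = 0.8 gives 99.9% with a half-width of ±7.4. This stands too, and is why a range is needed.

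No test is planned, and SAP 3.2.2.1 will report confidence intervals anyway, so no conclusion depends on the 81% and the achieved precision will be visible. That limits the harm. It does not supply a planning statement of precision, and it leaves the re-evaluation clause tied to the wrong quantity.

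Finally, differences between screening and Day -1 contain no variation in response to treatment. Protocol 1.7 says the amount of lead available for absorption is unknown and that the absorbed fraction depends on subject factors. Pre-dose differences alone would therefore tend to overstate precision.

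**Conclusion.** The point holds as a defect in the sample size justification. The 81% is not the power of a paired, one-group analysis of change in blood lead. On the survey SD of 24.7, power against 18.6 µg/l is about 97–99% at r = 0.5 (single and two-value baseline respectively) and above 99.9% for r = 0.8–0.95. The half-width for r = 0.8–0.95 is about ±5.2 to ±2.6 µg/l, against about ±2.2 to ±2.8 from assay error alone. These figures assume two-sided 5%, equal correlation among a subject's values and no added variance from differing responses to treatment.

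Three stronger readings should be resisted. The trial is not shown to be too small: the stated figure probably errs towards understating power. The documents do not say that the study can address only 18.6 µg/l; they present that value as a clinical margin. Nor do they establish that a rise several times smaller can be excluded: at r = 0.8 the rise for 81% power is 7.4 µg/l with the two-value baseline and 8.5 with a single one, a little under half the margin.

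**What to change.** In Protocol 8.1.2 and SAP 1.3.4, replace the power sentence with a one-sample (paired) calculation on change from baseline at n = 29. State:

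- alpha and sidedness;
- the assumed SD of change and its source;
- the expected 95% CI half-width for the mean change;
- the rise that can be excluded with about 80% power.

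Show the last two over a range of SDs. Treat the SD derived from the screening to Day -1 differences as a lower bound, and add a stated allowance for variation between subjects in their response to treatment. Tie any sample size re-evaluation under Protocol 8.2 and SAP 3.2.18 to the SD of change rather than to whether pre-dose lead matches the survey mean. Correct the survey SE or its printed interval so that they agree. Keep 35 enrolled.

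The cost is a recalculation, one rewritten paragraph in each document and a change to the re-evaluation clause. No extra subjects or samples are needed. The protocol change would need a written amendment with ethics approval under Protocol 12.1.1 unless it counts as purely administrative. The new figure will rest on an assumption about the SD of change, but an explicit one.
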